**Table AE 2 Adverse events by system organ class and preferred term (Full analysis set)**

System organ class Preferred term	NLX-112 (N=XX)		Placebo (N=XX)		Total (N=XX)	
	n (%)	m	n (%)	m	n (%)	m
Total	xx (xx%)	xx	xx (xx%)	xx	xx (xx%)	xx
[SOC 1]	xx (xx%)	xx	xx (xx%)	xx	xx (xx%)	xx
[SOC 1 PT 1]	xx (xx%)	xx	xx (xx%)	xx	xx (xx%)	xx
[SOC 1 PT 2]	xx (xx%)	xx	xx (xx%)	xx	xx (xx%)	xx
[SOC 1 PT ...]	xx (xx%)	xx	xx (xx%)	xx	xx (xx%)	xx
[SOC 2]	xx (xx%)	xx	xx (xx%)	xx	xx (xx%)	xx
[SOC 2 PT 1]	xx (xx%)	xx	xx (xx%)	xx	xx (xx%)	xx
[SOC 2 PT 2]	xx (xx%)	xx	xx (xx%)	xx	xx (xx%)	xx
[SOC 2 PT ...]	xx (xx%)	xx	xx (xx%)	xx	xx (xx%)	xx
[SOC ...]	xx (xx%)	xx	xx (xx%)	xx	xx (xx%)	xx
[SOC ... PT 1]	xx (xx%)	xx	xx (xx%)	xx	xx (xx%)	xx
[SOC ... PT 2]	xx (xx%)	xx	xx (xx%)	xx	xx (xx%)	xx
[SOC ... PT ...]	xx (xx%)	xx	xx (xx%)	xx	xx (xx%)	xx

Data based on the Full analysis set. n, number of subjects. m, number of events. Percentages are based on the number of subjects in the treatment period. The following events are coded with multiple terms and are represented as separate events in tables and listings: '[AE TERM 1], [AE TERM 2]'. See listings for detailed information. SAS program: [PROGRAM NAME].sas. Run by: [USERNAME] YYYY-MM-DDTHH:MM:SS. Data extracted at: YYYY-MM-DDTHH:MM:SS

If considered appropriate, produce the table above for SAEs only.

**Table AE 3 Overview of adverse events per titration period (Full analysis set)**

Use the same template as for Table AE 1, but include columns (NLX-112 and Placebo respectively) for the up-titration period (up to Visit 6), the stable dosing period (Visit 6 to Visit 7), the down-titration period (from Visit 7) and the Total column -> 7 results columns in all.

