#### 4.3 Randomization and number of subjects

On Day 1, patients were randomized to receive either NLX-112 or placebo with the ratio 2:1 for active treatment to placebo. This will give approximately 16 patients who received NLX-112 and 8 patients who received placebo in the study. In addition, approximately the same ratio was intended to be attained within each site. The study used competitive enrolment between 5 sites.

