**Table 1 Analysis sets**

Analysis set	Definition	Use of analysis set
Full analysis set (FAS)	The full analysis set (FAS) will comprise all randomized patients who were dosed.	Safety and efficacy evaluations. See section 10 below for more details.
Per protocol set (PPS)	The per protocol set (PPS) will consist of all patients included in the FAS population who do not have any major protocol violations assessed to compromise the analysis of study data. All protocol violations will be judged as major or minor prior to database lock. The patient must have an overall calculated compliance of 75% to be included in the PPS.	Efficacy evaluations. See section 10 below for more details.

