## 10.2.2 Primary endpoint(s)

### 10.2.2.1 Adverse events

**Table AE 1 Overview of adverse events (Full analysis set)**

	N LX-112 (N=XX)	Placebo (N=XX)		Total (N=XX)		
	n (%)	m	n (%)	m	n (%)	m
Any AE	xx (xx%)	xx	xx (xx%)	xx	xx (xx%)	xx
Any SAE	xx (xx%)	xx	xx (xx%)	xx	xx (xx%)	xx
Any AE leading to withdrawal from study	xx (xx%)	xx	xx (xx%)	xx	xx (xx%)	xx
Any AE leading to death	xx (xx%)	xx	xx (xx%)	xx	xx (xx%)	xx
Action taken with study drug	xx (xx%)	xx	xx (xx%)	xx	xx (xx%)	xx
Dose Not Changed	xx (xx%)	xx	xx (xx%)	xx	xx (xx%)	xx
Dose Rate Reduced	xx (xx%)	xx	xx (xx%)	xx	xx (xx%)	xx
Dose Reduced	xx (xx%)	xx	xx (xx%)	xx	xx (xx%)	xx
Drug Interrupted	xx (xx%)	xx	xx (xx%)	xx	xx (xx%)	xx
Drug Withdrawn	xx (xx%)	xx	xx (xx%)	xx	xx (xx%)	xx
Not Applicable	xx (xx%)	xx	xx (xx%)	xx	xx (xx%)	xx
Causality	xx (xx%)	xx	xx (xx%)	xx	xx (xx%)	xx
Unlikely	xx (xx%)	xx	xx (xx%)	xx	xx (xx%)	xx
Possible	xx (xx%)	xx	xx (xx%)	xx	xx (xx%)	xx
Probable	xx (xx%)	xx	xx (xx%)	xx	xx (xx%)	xx
Severity	xx (xx%)	xx	xx (xx%)	xx	xx (xx%)	xx
Mild	xx (xx%)	xx	xx (xx%)	xx	xx (xx%)	xx
Moderate	xx (xx%)	xx	xx (xx%)	xx	xx (xx%)	xx
Severe	xx (xx%)	xx	xx (xx%)	xx	xx (xx%)	xx
Life-Threatening	xx (xx%)	xx	xx (xx%)	xx	xx (xx%)	xx
Death	xx (xx%)	xx	xx (xx%)	xx	xx (xx%)	xx

Data based on the Full analysis set. N: number of subjects in treatment group. Percentages are based on N. n, number of subjects. m, number of events. The following AEs are coded with multiple MedDRA terms and are represented as separate AEs in tables and listings: '[AE TERM 1]', '[AE TERM 2]', '[AE TERM 3]'. See listings for detailed information. SAS program: [PROGRAM NAME].sas. Run by: [USERNAME] YYYY-MM-DDTHH:MM:SS. Data extracted at: YYYY-MM-DDTHH:MM:SS

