**Table AE 4 Adverse events by system organ class and preferred term per titration period (Full analysis set)**

Use the same template as for Table AE 2, but include columns (NLX-112 and Placebo respectively) for the up-titration period (up to Visit 6), the stable dosing period (Visit 6 to Visit 7), the down-titration period (from Visit 7) and the Total column -> 7 results columns in all.

10.2.2.2 *Physical examination*

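### Table AE 3 takes its per-period adverse event percentages on the whole arm, so patients already lost dilute the stable-dosing and down-titration columns

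*SAP*

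**What the plan says.** SAP section 9.1.1 promises adverse event tables by titration period but names no denominator. The denominators come only from the table shells in SAP section 10.2.2.1.

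- **Table AE 3** (overview by period) is built from AE 1: "Use the same template as for Table AE 1, but include columns (NLX-112 and Placebo respectively) for the up-titration period (up to Visit 6". The AE 1 footnote reads "N: number of subjects in treatment group. Percentages are based on N".
- **Table AE 4** (by system organ class and preferred term, by period) is built from AE 2: "Use the same template as for Table AE 2". The AE 2 footnote reads "Percentages are based on the number of subjects in the treatment period".
- **Period columns** start with up-titration to Visit 6 and continue with "the stable dosing period (Visit 6 to Visit 7), the down-titration period (from Visit 7) and the Total column -> 7 results columns in all".
- **Analysis set** (SAP Table 1): "The full analysis set (FAS) will comprise all randomized patients who were dosed". Someone who leaves during up-titration therefore stays in the arm N.

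Neither AE 3 nor AE 4 asks for a new N or a revised footnote. The shells for Tables UD 3 to UD 5 do ask the programmer to revise the explanatory footnote, so the SAP gives that instruction where it is wanted.

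**The concern.** A percentage in a column headed stable dosing will be read as the share of patients in that period who had an event. Under the AE 1 rule it is the share of everyone ever dosed in the arm. A patient who left in week 2 then sits in the denominator for weeks 5 and 6 with no chance of adding to the numerator.

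Losses before Visit 6 are foreseen. Protocol section 8.1 lets patients with intolerable events in up-titration withdraw, and section 9.3 allows extra patients because of drop-outs. Under SAP section 4.4, patients withdrawn for events judged possibly or probably related to treatment are not replaced. A dosed patient who is replaced still remains in the full analysis set, so N exceeds the number at risk in that case too.

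Adverse event frequency is a primary endpoint, and AE 3 and AE 4 are the only planned adverse event tables that separate stable dosing from titration.

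**Working it through.** The documents state no per-period event rate and no drop-out rate, so there is no planned figure to reproduce. Two layout checks agree with the SAP: 24 patients at 2:1 give 24 × 2/3 = 16 and 24 × 1/3 = 8, and 3 periods × 2 arms + 1 Total = 7 columns.

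**Inputs.** N = 16 for NLX-112 and 8 for placebo (SAP section 4.3: "This will give approximately 16 patients who received NLX-112 and 8 patients who received placebo in the study"). L, the number lost before the period starts, is assumed: 0 to 6 of 16 on NLX-112 and 0 to 3 of 8 on placebo. x is the number of patients with an event in the period.

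**Formulas.**
- AE 3 as written: x / N.
- Among patients still in the period: x / (N − L).
- Ratio of the first to the second: (N − L) / N = 1 − L/N, so the relative understatement is L/N.

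**NLX-112, N = 16, x = 3:**

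| L (assumed) | Still in period | AE 3: 3/16 | 3/(16 − L) | Understatement L/16 |
|---|---|---|---|---|
| 0 | 16 | 18.75% | 18.75% | 0% |
| 1 | 15 | 18.75% | 20.0% | 6.25% |
| 2 | 14 | 18.75% | 21.4% | 12.5% |
| 4 | 12 | 18.75% | 25.0% | 25% |
| 6 | 10 | 18.75% | 30.0% | 37.5% |

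**Placebo, N = 8:** L = 1, 2 or 3 gives an understatement of 12.5%, 25% or 37.5%.

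**Between arms.** Suppose the rate among patients still in the period is 50% in both arms.
- Only NLX-112 loses patients (2, 4 or 6): AE 3 shows 50 × 14/16 = 43.75%, 50 × 12/16 = 37.5% or 50 × 10/16 = 31.25%, against 50% on placebo. The false gap of 6.25 to 18.75 points favours NLX-112.
- One loss in each arm: 50 × 15/16 = 46.9% on NLX-112 and 50 × 7/8 = 43.75% on placebo. The false gap of about 3 points goes against NLX-112.
- Two of 16 and one of 8: both arms show 43.75%, with no false gap.

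What matters is the proportion lost, not the number.

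**Table AE 4.** Its inherited footnote has two readings. If the treatment period means the titration period, AE 4 uses x / (N − L). With L = 4 and x = 3 it prints 25.0% where AE 3 prints 18.75% for the same patients. If it means the whole treatment phase, AE 4 uses x / N as well, and both tables are diluted.

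**The case against.** The strongest objection is that the conflict between AE 3 and AE 4 is not certain. The AE 2 footnote also appears under the medical history and medication tables (MH 1, CM 1, CM 2), which have no period columns. There it looks like standard wording for treated patients in the arm. This stands: a reader might infer that the two tables must disagree, but that is only the natural reading of the footnote once it sits under period columns. It does not rescue AE 3, whose whole-arm rule is explicit, and on the alternative reading AE 4 shares the fault.

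Second, the effect may be small. No drop-out rate is given, and patients with intolerable events may step back to the previous dose instead of leaving. In the earlier 12-week diabetic neuropathy study (protocol section 6.1.3; 124 patients, 2 mg/day), only one NLX-112 patient withdrew for a treatment-emergent event. That is a different population, but nothing in the documents supports a loss as large as 4 of 16. The point about size stands.

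Third, a reader might infer that the table is biased in favour of NLX-112. The documents do not establish a direction, because under 2:1 allocation a single placebo loss dilutes as much as two NLX-112 losses.

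Fourth, a reader might take the stable-dosing column as the rate at 2 mg/day. SAP section 4.1 keeps patients at a lower tolerated dose in that period, so no choice of denominator makes it so.

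Last, overall frequency, intensity and seriousness come from AE 1 and AE 2, which are unaffected. AE 3 still prints patient and event counts, and the listings would let a reader rebuild the rates for about 24 patients. That limits the harm but does not make the printed percentage right.

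**Conclusion.** The point holds for AE 3. As written, its stable-dosing and down-titration percentages are too low by the relative fraction L/N in any arm that has lost patients before the period. For NLX-112 this is 6.25%, 12.5% or 25% for an assumed 1, 2 or 4 losses from 16. The between-arm comparison is distorted when the proportions lost differ, and either arm may gain. AE 4 needs its denominator stated on either reading of its footnote.

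The size rests entirely on the assumed losses. If nobody leaves before Visit 7, AE 3 and AE 4 are correct as they stand. The up-titration columns, all counts, and Tables AE 1 and AE 2 are not affected. It is worth correcting because the tables describe a primary endpoint and the correction is almost free.

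**What to change.** In AE 3 and AE 4, use one denominator: the patients in the arm still under adverse event observation at the start of that period. Print this N at the head of each period column and update both footnotes to say so. Keep the arm N for AE 1 and AE 2, and the full analysis set N for the Total column.

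Do not define the denominator as patients who took at least one dose in the period. The last column runs from Visit 7 with no stated end, and protocol section 11.2.1.6 collects events to the end-of-study visit, scheduled at Day 70, while dosing ends on Day 56. A patient who takes no dose after Visit 7 but reports a later event would be in the numerator and outside the denominator. For that column, count patients in follow-up whether or not they took a further dose.

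The cost is a change to column headers and footnotes in two shells. It needs no new data, since visit attendance and discontinuation are already to be listed.

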## 6.3 Risk/benefit assessment

### 6.3.1 *Potential risks*

In prior clinical studies of NLX-112, the most frequently reported undesirable treatment effects were dizziness, somnolence, headache, nausea, and malaise; these effects are consistent with the pharmacological profile of NLX-112. These effects occurred mostly during the first days of treatment and were most frequent at the highest doses of study drug (i.e.,  $\geq 3.0$  mg/day).

The study of the tolerability and safety of NLX-112 administered as multiple doses after an adaptive dose titration in healthy subjects showed that progressive up-titration, and adjusting dose escalation based on individual tolerability, allowed some healthy men to tolerate 10 mg/day, when administered as 5 mg BID.

Abrupt discontinuation of NLX-112 after multiple daily dosing of 3.0 mg/day or higher was associated with the sporadic occurrence of withdrawal symptoms (mainly nightmare, anxiety, hallucination, and euphoric mood) which were reduced in severity with progressive down-titration.

Undesirable hemodynamic effects (i.e., decrease in blood pressure and postural hypotension) were observed in some elderly subjects.

Thus, based on prior human experience, NLX-112 can be safely administered up to the dose of 3.0 mg/day (1.5 mg BID), with a progressive up-titration to maximize the tolerability of the drug and a down-titration regimen after the fixed dose period to minimize potential withdrawal symptoms.

In cases of accidental overdose, standard supportive measures should be adopted as required. For further information regarding overdosing, refer to Section 11.2.1.17.

Each patient will be provided with a patient information card with information about the patient's participation in a study, see Section 14.4.

The Principal Investigator at the research clinic will ascertain that adequate facilities and procedures are available to handle emergency situations should they occur during the study.

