**Down-titration period (2 weeks, down-titration by 0.25 mg/day every 2 days):**

- Days 43-44 (start of down-titration period [1.75 mg/day])
- Days 45-46 (1.5 mg/day)
- Days 47-48 (1.25 mg/day)
- Days 49-50 (1 mg/day)
- Days 51-52 (0.75 mg/day)
- Days 53-54 (0.5 mg/day)
- Days 55-56 (0.25 mg/day)

Patients in the placebo arm will follow the same dose escalation, constant dose and down-titration schedule, but will be taking the matching placebo tablets. Patients who have intolerable AEs during the 28-day up-titration period will be allowed to return to the previous tolerated dose at the discretion of the Investigator, or they may withdraw from the study if they so choose.

Each patient is expected to participate in the study for approximately 10 weeks, not including screening. Patients will be treated with IMP for a total of 8 weeks (56 days).

The timing of events is summarized in Table 8.1-1. Study assessments are described in Section 11.

Table 8.1-1 Schedule of events

Study visit number		Visit 1	Visit 2	Visit 3	Visit 4	Visit 5	Visit 6	Visit 7	Visit 8	Visit 9
Study period		Screening	Baseline	Phone Safety Visit	Clinic Safety Visit	Clinic Safety Visit	Clinic Efficacy Visit	Clinic Efficacy Visits	Phone Safety Visit	Follow-up Clinic Visit 
Study day	Protocol Section	Day -28 to Day -5	Day 1	Day 7 ±1 day	Day 14 ±2 days	Day 21 ±2 days	Day 28 ±2 days	Day 42 ±2 days	Day 49 ±2 days	Day 70 ±7 days
Informed Consent	14.3	X								
Eligibility criteria	9.4 & 9.5	X	X 							
Demographics	11.1.3	X								
Vital signs 	11.2.3	X	X		X	X	X	X		X
Physical examination	11.2.2	X								X
Body weight and height 	11.1.4	X								X
Hoehn and Yahr scale 	11.1.8	X	X							
Medical and psychiatric history	11.1.5	X								
Pregnancy test 	11.1.7	X	X							X
12-lead ECG	11.2.4	X	X		X	X	X	X		X
Safety laboratory 	11.2.6	X	X		X	X	X	X		X
MMSE	11.1.9	X								
C-SSRS 	11.2.5	X	X		X	X	X	X		X
UPDRS 	11.3.1	X	X				X	X		X
Diary and wearable device training	11.3.3&11.3.6	X	X							
Randomization	9.9		X							
Study drug dispensing	10.5		X				X	X		
Treatment (Day 1 - Day 56)	10.6					X				

Study visit number		Visit 1	Visit 2	Visit 3	Visit 4	Visit 5	Visit 6	Visit 7	Visit 8	Visit 9
Study period		Screening	Baseline	Phone Safety Visit	Clinic Safety Visit	Clinic Safety Visit	Clinic Efficacy Visit	Clinic Efficacy Visits	Phone Safety Visit	Follow-up Clinic Visit 

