### 9.1 Analysis of the primary endpoints

#### 9.1.1 *Adverse events*

An overview of all AEs, including SAEs, intensity, relationship to IMP, and deaths will be presented by treatment. Incidence of AEs will be summarized by SOC and PT by treatment. Separate tables will be provided, if relevant, for serious AEs (SAEs) or events leading to withdrawal from study. Separate tables will be provided with summaries per titration period as well (up-titration, stable dosing and down-titration).

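### The down-titration adverse-event column starts at Visit 7 and has no stated end, so about half of it is follow-up after the last dose

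*SAP*

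**What the plan says.** SAP section 9.1.1 announces the breakdown: "Separate tables will be provided with summaries per titration period as well (up-titration, stable dosing and down-titration"). The shells in SAP section 10.2.2.1 implement it with visits as boundaries. Up-titration runs up to Visit 6. Table AE 3 then sets "the stable dosing period (Visit 6 to Visit 7), the down-titration period (from Visit 7"). Table AE 4 repeats the last boundary: "the down-titration period (from Visit 7) and the Total column". Table AE 3 fixes the layout at "7 results columns in all".

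The protocol gives the taper an end. Its down-titration schedule (Synopsis and section 8.1) covers Days 43 to 56, with the last step at "Days 55-56 (0.25 mg/day"), and total treatment is 56 days. Under protocol section 11.2.1.6, AE recording starts with the first dose and closes at the end-of-study visit. The schedule of events (Table 8.1-1) puts Visit 7 at Day 42 ±2 and Visit 9 at Day 70 ±7.

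**The concern.** Safety and tolerability are the primary objective, and the per-period tables sit under the primary endpoint. Down-titration was included partly because of withdrawal effects: protocol section 6.1.3 gives preventing withdrawal symptoms as its purpose. In the earlier diabetic neuropathy study CP201, which also tapered, drug-related withdrawal syndrome was reported in 4 of 114 patients at 2 mg/day and 1 of 112 on placebo (protocol Table 6.1-1).

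A reader of AE 3 or AE 4 will want to know whether late events arose while the dose was falling or after dosing had stopped. A column named after the taper that also holds the post-treatment fortnight cannot answer that, and it attributes follow-up events to the wrong phase. It also spans twice the time of the stable-dosing column beside it, so raw counts in the two columns are not like for like.

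**Working it through.** **Reproducing the documents' own figures**
- Taper: 7 steps × 2 days = 14 days (Days 43 to 56).
- Treatment: 7 × 4 + 14 + 14 = 56 days.
- Result columns: 3 periods × 2 arms + 1 Total = 7.

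All three agree with the documents. The column count confirms that there is no fourth period.

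**Share of the last column after the last dose**

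Share = (Visit 9 day − last dose day) / (Visit 9 day − Visit 7 day), with Visit 7 at Day 42 and last dose on Day 56:
- Visit 9 at Day 70: (70 − 56)/(70 − 42) = 14/28 = 50%.
- Visit 9 at Day 63: 7/21 = 33%.
- Visit 9 at Day 77: 21/35 = 60%.

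Letting Visit 7 also move over Days 40 to 44, with last dose either on Day 56 or 14 days after Visit 7, the range is 5/19 = 26% to 21/33 = 64%.

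**Patients on a lower maximum dose**

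The documents list a taper only from 2 mg/day. If, as an assumption, such patients stepped down 0.25 mg every 2 days from Visit 7, dosing would end sooner. From 1.5 mg/day the taper lasts 10 days and the share is 18/28 = 64%. From 1 mg/day it lasts 6 days and the share is 22/28 = 79%.

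**Length against the neighbouring column**

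Stable dosing, Day 28 to Day 42, is 14 days; Day 42 to Day 70 is 28 days; the ratio is 2.

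**How often this could matter**

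Taking the CP201 rates as an assumption, the chance of at least one withdrawal-syndrome event is 1 − (1 − 4/114)^16 = 44% with 16 patients on NLX-112 and 1 − (1 − 1/112)^8 = 7% with 8 on placebo.

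**After the fix**

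Down-titration is Days 43 to 56 (14 days). Follow-up is Days 57 to 70 (14 days; 7 to 21 over the Visit 9 window). Columns: 4 × 2 + 1 = 9.

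**The case against.** The strongest reply is that nothing is lost. AE start and stop dates are recorded (protocol section 11.2.1.12), and the SAP plans patient-level listings of AEs (16.2.7-1) and IMP administration (16.2.5-3). With about 24 patients, each late event can be placed by hand. This stands. A reader might infer that withdrawal events cannot be separated at all, but that is true only of the summary tables.

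Both arms share the same column and no test between periods is planned, so the length of the column does not bias the comparison with placebo. This also stands.

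The mean half-life is 34 to 41 h (protocol section 6.1.3), so five half-lives take 5 × 34/24 = 7.1 to 5 × 41/24 = 8.5 days. After the last dose means no dosing, not no exposure. Withdrawal symptoms can also start on a falling dose, so a date split shows timing and not cause.

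It could be argued that the label alone limits the column to the protocol's Days 43 to 56. Then AEs after Day 56 would have no period column, so the text needs an end on either reading.

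Three stronger inferences are not supported:
- **The Day 29 step to 2 mg/day is misfiled under stable dosing.** The protocol's own constant-dose period is Days 29 to 42, so nominal Visits 6 and 7 match it. Only the ±2-day visit windows remain.
- **AE 3 and AE 4 use conflicting denominators.** AE 1 says "Percentages are based on N" and AE 2 says "Percentages are based on the number of subjects in the treatment period". The AE 2 wording also stands under Tables MH 1, CM 1 and CM 2, which have no periods, so it is probably loose wording for the treatment group. It needs clarifying, but no conflict is shown.
- **The protocol's withdrawal warning applies directly.** In section 6.3.1 it is abrupt stopping after 3.0 mg/day or more that "was associated with the sporadic occurrence of withdrawal symptoms". This trial is capped at 2 mg/day and tapers. The CP201 figures are closer, but do not say whether events arose during or after the taper.

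**Conclusion.** The concern holds for the planned tables. As written, AE 3 and AE 4 count post-treatment AEs under down-titration. Nominally 14 of the column's 28 days follow the last dose (50%; 33% to 60% over the Visit 9 window). This assumes dosing to Day 56 as scheduled and that the column closes where AE collection closes, at Visit 9. The three adjoining periods with no follow-up column make that the natural reading.

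The weight is modest. This is a classification and display fault in descriptive tables of about 16 against 8 patients, recoverable from listings. It still merits correction, because the tables report the primary endpoint and a phase label should mean what the protocol means by it.

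**What to change.** In SAP section 9.1.1 and Tables AE 3 and AE 4:
- Assign each AE to a period by its onset date.
- Start down-titration at the beginning of the scheduled taper after stable dosing, not at any earlier dose reduction. The protocol lets patients return to a previous tolerated dose during up-titration, and that return should not open the down-titration column. This rule also settles where Visit 7 itself belongs, since the present wording puts it in two periods.
- End down-titration at the patient's last IMP date. If that date is not recorded, use the scheduled end of the 14-day taper. The fallback is needed because SAP section 5.4 names actual days per dosing stage only for up-titration and stable dosing.
- Add a post-treatment follow-up column per arm, from the day after last IMP to Visit 9, giving 9 result columns.
- Put AEs that begin after early discontinuation of IMP in follow-up.
- State one denominator for both tables, as a clarification only.

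AE onset dates are already collected and an IMP administration listing is already planned, so no new data are needed. The cost is shell wording, two extra columns and slightly wider tables. The added column separates events by time of onset; it does not establish cause.
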